5.4.3. Concomitant Medications

Prior and concomitant medications will be coded using the World Health Organization (WHO) dictionary version March 2018. Prior and concomitant medications will be presented in a data listing. Concomitant medications will additionally be summarized by treatment group.

5.4.4. Other Safety Analyses

Descriptive summaries of vital signs data including body temperature, pulse, respiratory rate, and blood pressure (systolic and diastolic) and respective changes from Baseline, will be presented by time point and treatment group. The number and percentage of patients with PCS vital signs per the table below, as determined in the eCRF, occurring post-baseline will

also be summarized by time point and treatment group. All vital signs will be listed with clinically significant values flagged, as well as for patients with any PCS results.

CRITERIA FOR POTENTIALLY CLINICALLY SIGNIFICANT VITAL SIGNS

Parameter	Flag	Criteria
		Observed Value
Systolic blood pressure (mm Hg)	High	≥ 150
	Low	≤ 90
Diastolic blood pressure (mm Hg)	High	≥ 100
	Low	≤ 50
Pulse rate (bpm)	High	≥ 110
	Low	≤ 50
Temperature (°C)	High	≥ 38
	Low	< 35

Electrocardiogram (ECG) variables and their change from baseline will be summarized with descriptive statistics by time point and treatment group. ECG variables will include heart rate, PR interval, QRS interval, QT interval, and QTc interval corrected for heart rate using QTcF. QTcF values will also be tabulated for their absolute values and tabulated relative to baseline measurements in order to detect individual QTcF changes. Additionally, the number and percentage of patients with PCS values defined in the table below

Use header of the convention table for all relevant safety parameters.

Criteria for Potentially Clinically Significant ECG Parameters

Parameter	Flag	Criteria	
		Observed Value	Change from Baseline or Observed Value
Heart Rate (bpm)	High	> 110	
	Low	≤ 50	

QTcF ^a Interval (msec)	High Male	> 450	30-60, > 60, > 500
	High Female	> 470	
QRS Interval (msec)	High	> 120	
PR Interval (msec)	High	> 220	

^a QTc interval (Fridericia's) is derived as: $QTcF = QT \text{ Interval (msec)} / (RR \text{ (msec)/1000})^{1/3}$

For these summaries, worst-case assignments will be made to ensure patients with such values are not counted more than once. For example, a patient with QTcF interval > 500 msec will count once in the > 500 msec category and will not appear in the > 450 or > 480 msec categories. Similar conventions will be used for the 30 to 60 and > 60 msec categories. All ECG analyses will be based on the average of triplicate measurements.

Important abnormalities in ECG waveform that are changes from Baseline readings will also be reported in a listing. All ECG will be listed with clinically significant values flagged, as well as for patients with any PCS results.

All physical examination results will be listed.

Results from the Columbia-Suicide Severity Rating Scale (C-SSRS) will be summarized by visit and treatment group. All C-SSRS results will also be reported in a listing.

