4.2. Exclusion Criteria

Potential patients who meet any of the following criteria will be excluded from participating in the study:

1. A DSM-5 diagnosis of current (active): panic disorder, obsessive compulsive disorder (OCD), post-traumatic stress disorder (PTSD), anorexia nervosa, or bulimia nervosa.
2. History or current diagnosis of a psychotic disorder, bipolar disorder, mental retardation, or borderline personality disorders, mood disorder with postpartum onset, somatoform disorders, fibromyalgia, or idiopathic medical conditions.
3. At significant clinical risk for suicidal or violent behavior.
4. History of treatment within last 6 months with electroconvulsive therapy (ECT), Vagus Nerve Stimulation (VNS), Deep Brain Stimulation (DBS), or Transcranial Magnetic Stimulation (TMS).
5. Potential patient who in the opinion of the investigator should not discontinue, or participate in washout of a prohibited concomitant medication.
6. Potential patient who demonstrate a greater than 25% decrease in depressive symptoms as reflected by the IDS-SR₃₀ total score from Screening visit to Baseline visit.

-
7. Active cardiovascular disease (including but not limited to: atrial fibrillation or flutter, second and third-degree atrioventricular heart block, resting supraventricular tachycardia >100 beats per minute, unstable ischemic heart disease, valvular abnormality, sick sinus syndrome or other condition requiring pacemaker) or diastolic blood pressure > 105 mmHg.
 8. Any serious, untreated, or unstable illnesses, such as: liver or renal insufficiency.
 9. Any significant pulmonary, endocrine, or metabolic disturbances.
 10. Documented disease of the central nervous system that could interfere with the study assessments (including but not limited to: stroke, tumor, multiple sclerosis, Parkinson's disease, Alzheimer's disease, Huntington's disease, seizure disorder requiring current anti-convulsants, traumatic brain injury or trauma, and neurosyphilis).
 11. Hypothyroidism or hyperthyroidism, unless stabilized by appropriate medication for at least 3 months prior to Screening (a normal thyroid-stimulating hormone [TSH] is required prior to randomization at Baseline).
 12. Any medical condition that can potentially alter oral enteral absorption (e.g., gastrectomy), metabolism (e.g., liver failure), or excretion (e.g., renal failure) of the study drug.

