 13. History of alcohol or substance use disorders (except nicotine and caffeine) meeting DSM-5 criteria within 1-year prior to Screening visit.
 14. Positive alcohol and urine drug screen for opiates, cocaine, barbiturates, tetrahydrocannabinol, methadone, tricyclic antidepressants, benzodiazepines, and amphetamine/methamphetamine at Screening or Baseline. Patients with positive testing at Screening due to prescribed benzodiazepines, tricyclic antidepressants, barbiturates or opiates are accepted but must test negative at Baseline (Visit 2).
 15. Male patients who have pregnant partners.
 16. Female patients who are breast-feeding.
 17. Received an experimental drug or used an experimental medical device within 60 days before the planned start of treatment (Day 1) or have participated in 2 or more clinical trials in the previous 2 years.
 18. QTcF interval at Screening or Baseline greater than 450 msec for males and 470 msec for females.
 19. Patients requiring treatment with drugs likely to prolong QT.
 20. Patients with known hypersensitivity to MIN-117 or placebo or their excipients (refer to section 13.1 p. 64 of the protocol).
 21. Positive hepatitis B surface antigen, or hepatitis C antibody or Human Immunodeficiency Virus (HIV) 1 and 2 antibodies at Screening.
 22. Employees of the investigator or study center, when the employee has direct involvement in the proposed study or other studies under the direction of that investigator or study center; also family members of the employee or the investigator.

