 - 14.3.1.5 Treatment-Emergent Fatal Adverse Events by System Organ Classification and Preferred Term, Safety Population
 - 14.3.2.1 Treatment-Emergent Serious Adverse Events by System Organ Classification and Preferred Term, Safety Population
 - 14.3.4.1 Clinical Laboratory Hematology Parameters by Time Point, Safety Population
 - 14.3.4.2 Clinical Laboratory Chemistry Parameters by Time Point, Safety Population
 - 14.3.4.3.1 Clinically Significant Laboratory Values, Safety Population
 - 14.3.4.3.2 Clinically Significant and Potentially Clinically Significant Laboratory Values, Safety Population
 - 14.3.4.4 Clinical Laboratory Parameter Shifts from Study Baseline to Week 6, Safety Population
 - 14.3.5.1 Vital Signs by Time Point, Safety Population
 - 14.3.5.2.1 Patients with Clinically Significant Vital Signs Occurring Post-Baseline, Safety Population
 - 14.3.5.2.2 Patients with Clinically Significant or Potentially Clinically Significant Vital Signs Occurring Post-Baseline, Safety Population
 - 14.3.5.3.1 12-Lead ECG Assessments by Time Point, Safety Population
 - 14.3.5.3.2 Summary of QTcF (msec) Categories, Safety Population
 - 14.3.5.4 Patients with Significant ECG Abnormalities Occurring Post-Baseline, Safety Population
 - 14.3.6.1 Summary of C-SSRS by Visit, Safety Population

Data Listings

- 16.2.1 Patient Disposition
 - 16.2.2.1 Protocol Deviations
 - 16.2.2.2 Inclusion/Exclusion Criteria
 - 16.2.4.1 Demographics
 - 16.2.4.2 Medical and Surgical History
 - 16.2.5.1 Study Drug Administration
 - 16.2.5.2 Prior and Concomitant Medications
 - 16.2.5.3.1 Pharmacokinetic Plasma Concentrations
 - 16.2.6.1 MADRS Rating Scale
 - 16.2.6.2 CGI-S and CGI-I Questionnaires
 - 16.2.6.3 HAM-A Questionnaires
 - 16.2.6.4 IDS-SR₃₀ Questionnaires
 - 16.2.6.5 SHAPS Questionnaires
 - 16.2.6.6 DSST Questionnaires
 - 16.2.6.7 PSS Questionnaires
 - 16.2.6.8 A-SEX Questionnaires
 - 16.2.6.9 C-SSRS Questionnaires
-

16.2.6.10	Somno-Art Sleep Parameters
16.2.7	Adverse Events
16.2.8.1.1	Laboratory Data – Chemistry
16.2.8.1.2	Laboratory Data – Hematology
16.2.8.1.3	Laboratory Data – Urinalysis
16.2.8.1.4	Laboratory Data – Other
16.2.8.1.5	Laboratory Results Outside Reference Range
16.2.8.1.6	Potentially Clinically Significant Laboratory Results
16.2.8.2.1	Vital Signs
16.2.8.2.2	Weight, Height and BMI
16.2.8.3	Physical Examinations
16.2.8.4	12-Lead ECG Findings

Figures

14.2.1.1.5	Change from Baseline in MADRS by Visit, ITT Population

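### Post-baseline counts of potentially clinically significant vital signs ignore Baseline, so unchanged pre-existing values (such as diastolic 100-105 mmHg) can dilute the dose-placebo contrast

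*SAP*

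**What the plan says.** **Vital signs.** SAP section 5.4.4 defines a count, split by visit and arm, in these words: "The number and percentage of patients with PCS vital signs per the table below, as determined in the eCRF, occurring post-baseline". The table it refers to, "CRITERIA FOR POTENTIALLY CLINICALLY SIGNIFICANT VITAL SIGNS", has criteria for the observed value only:
- systolic >= 150 or <= 90 mm Hg
- diastolic >= 100 or <= 50 mm Hg
- pulse >= 110 or <= 50 bpm
- temperature >= 38 or < 35 °C

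Neither the sentence nor the table asks what the patient's value was at Baseline.

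**ECG.** The same section sets PCS limits for heart rate (> 110 or <= 50 bpm), QRS (> 120 msec), PR (> 220 msec) and QTcF (> 450 msec in men, > 470 in women). Only QTcF also has change categories (30-60 and > 60 msec). The sentence that introduces the ECG count breaks off before its verb. Its time window can be read only from the title of Table 14.3.5.4 in SAP section 9: "Patients with Significant ECG Abnormalities Occurring Post-Baseline, Safety Population".

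**Entry.** Protocol section 4.2, exclusion 7, bars "diastolic blood pressure > 105 mmHg" and, among conduction disorders, "second and third-degree atrioventricular heart block". Exclusion 18 bars "QTcF interval at Screening or Baseline greater than 450 msec for males and 470 msec for females". Inclusion 14 (section 4.1) asks for good general health, with vital signs and ECG left to the investigator's judgement and no numbers given.

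**Elsewhere in the SAP.** Section 5.4.2 does refer to Baseline for laboratory data. Clinically significant abnormalities are counted as treatment-emergent, shifts from Baseline to Week 6 are tabulated, and the low hematocrit criterion also requires a fall from Baseline.

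**The concern.** A patient who enters at 102 mmHg diastolic and never changes satisfies every entry criterion that carries a number, and then counts as PCS at each later visit. The same can happen with a stable PR above 220 msec or QRS above 120 msec, since first-degree block and QRS width have no entry limit. Attachment 1 allows some chronic antihypertensives, so treated hypertension will be present.

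Vital signs are a reasonable place to look for a drug effect here. Protocol section 1.2 describes alpha-1 antagonism. Section 1.4 reports, for the 3 mg dose in the multiple-dose study, slightly lower supine diastolic pressure, more abnormal orthostatic tests and a heart-rate rise of up to 15.6 bpm, against 1.083 on placebo. The PCS table is the main categorical display of such effects, and a background of unchanged values makes it less informative.

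**Working it through.** **1. Entry limits against PCS limits**

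| Measure | Admitted by a numeric limit | PCS | Overlap |
|---|---|---|---|
| Diastolic, high | <= 105 mmHg | >= 100 | 100-105 mmHg |
| Systolic, high or low | no numeric limit | >= 150 or <= 90 | possible, subject to inclusion 14 |
| Diastolic, low | no numeric limit | <= 50 | possible, subject to inclusion 14 |
| Low pulse / heart rate | no numeric limit | <= 50 | possible, subject to inclusion 14 and exclusion 7 |
| PR, QRS | no numeric limit | > 220, > 120 msec | possible, subject to inclusion 14 and exclusion 7 |
| QTcF, men | <= 450 msec | > 450 | none |
| QTcF, women | <= 470 msec | > 470 | none |

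High diastolic pressure is the only overlap that follows from two stated numbers. For the other rows with possible overlap, the point is only that no entry number prevents it. One side note on QTcF: the protocol's sex-neutral > 450 msec category (section 10.8.4) would include an eligible woman at 451-470 msec at Baseline, but this is not the SAP's PCS limit.

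**2. Arm sizes**

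The plan states no PCS rate, so there is none to reproduce. The arm sizes do reproduce. A 4-point difference, SD 9, two-sided 0.025 per comparison, 80% power and 2:1 allocation give 145 and 73 evaluable (stated 146 and 73; power at 146/73 is 80.5%). Then 146/0.9 = 162.2 and 73/0.9 = 81.1, stated as 162 and 81.

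**3. Effect of carry-over**

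Let b be the share already PCS at Baseline on a given row, all staying PCS, and e the new-onset rate in the rest. The planned count then estimates p = b + (1 - b)e in each arm. The difference is (1 - b)(e1 - e0), and SE = sqrt(p1(1 - p1)/81 + p0(1 - p0)/162).

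Assume e0 = 1% and e1 = 3%. At b = 0.05, p1 = 0.05 + 0.95 x 0.03 = 7.85% and p0 = 0.05 + 0.95 x 0.01 = 5.95%.

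| b (about n of 324) | Dose v placebo, % | Difference, points | Risk ratio | SE, points (relative to b = 0) |
|---|---|---|---|---|
| 0 (0) | 3.0 v 1.0 | 2.00 | 3.00 | 2.05 (1.00) |
| 2% (6) | 4.9 v 3.0 | 1.96 | 1.66 | 2.75 (1.34) |
| 5% (16) | 7.9 v 6.0 | 1.90 | 1.32 | 3.52 (1.72) |
| 10% (32) | 12.7 v 10.9 | 1.80 | 1.17 | 4.44 (2.16) |

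A count restricted to patients not PCS at Baseline keeps 3% v 1%. Its SE is 2.05/sqrt(1 - b), at most 2.05/sqrt(0.90) = 2.16 points, or 1.05 times the b = 0 value.

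**4. A larger assumed effect**

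With new onset of 5% v 15%, the risk ratio falls from 3.00 to 2.66, 2.24, 1.97 and 1.62 at b = 1, 3, 5 and 10%. Nominal two-sided 5% power falls from 73% to 69, 61, 55 and 42%. The difference goes from 10.0 to 9.9, 9.7, 9.5 and 9.0 points. Power serves only as a measure of lost information, because no test is planned.

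**The case against.** Much of the case on the other side stands.

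- **Direction.** The one explicit overlap is high diastolic pressure, whereas alpha-1 antagonism and the section 1.4 findings point to low pressure and raised heart rate. High and low are flagged separately, so a patient at 102 mmHg adds nothing to the low row. Orthostatic tests are not part of these counts, since pressure is taken supine. The earlier clinical data described in the protocol show no PR or QRS signal.
- **Labelling.** A reader might infer that pre-existing abnormalities will be presented as on-treatment or adverse events. The documents do not support that: the SAP calls them PCS values occurring post-baseline, and Protocol section 10.8.3 asks only for the percentage beyond set limits.
- **Masking.** A reader might also infer that a real signal would be hidden. That is not shown. Randomization balances carry-over in expectation, and the difference shrinks only by the factor 1 - b. In the 1% v 3% example, even b = 0 gives 2.0 points with SE 2.05, so there is little signal to hide. The SAP plans neither a ratio nor a test.
- **Other displays.** Changes from Baseline are summarized for all vital signs and ECG intervals, PCS patients are listed, and placebo shows the background rate.
- **Screening.** Inclusion 14 may remove many such patients, and the eCRF determination named in the SAP cannot be seen.

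What does not stand is that these make the count adequate. Mean changes barely register a few new outliers, and listings leave the reader to rebuild the table by hand. Inclusion 14 has no numbers and does not close the 100-105 mmHg overlap.

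**Conclusion.** The point holds as a limited weakness in descriptive safety tables. The vital-sign PCS count has no Baseline condition, diastolic 100-105 mmHg is admitted and already PCS, and no numeric entry limit rules out the same for systolic pressure, low pulse, PR or QRS. For ECG the counting rule is inferred from a table title, because the SAP sentence is incomplete. QTcF is outside the point, so it should not be read as covering ECG as a whole.

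The consequence is dilution common to all arms, not directional bias. It is marked on the ratio scale and small on the difference scale. All of its size rests on assumed new-onset rates, an assumed Baseline prevalence of 2-10% and full persistence. With lower prevalence or values that regress, the effect is smaller.

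**What to change.** In SAP section 5.4.4 and Tables 14.3.5.2.2 and 14.3.5.4:

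1. Keep the any-post-baseline PCS count.
2. Add a treatment-emergent PCS count for vital signs, heart rate, PR and QRS. It counts patients not beyond the same limit in the same direction at Baseline, with those patients as the denominator.
3. Show the number already PCS at Baseline in each arm.
4. Add a Baseline-by-worst-post-baseline shift display. Simply removing Baseline-PCS patients would hide anyone who worsens, for example from 102 to 125 mmHg diastolic.
5. Complete the ECG PCS sentence, stating what is counted and over which visits.

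No entry criterion changes. The cost is a few SAP sentences, some extra table programming and slightly smaller denominators for the added count: at 10% already PCS, about 73 of 81 and 146 of 162.

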10.8.4. Electrocardiogram (ECG)

The effects on cardiovascular variables will be evaluated by means of descriptive statistics and frequency tabulations. These tables will include observed values and changes from Baseline values (the pre-dose ECG will be used as Baseline) to allow detection of clinically relevant changes in individuals.

The ECG variables that will be analyzed are heart rate, PR interval, QRS interval, QT interval, and QTc interval corrected for heart rate using QTcF. QTcF values will be tabulated for their absolute values and also tabulated relative to Baseline measurements in order to detect individual QTcF changes (ICH-E14 2005).

Descriptive statistics of QTcF intervals and changes from Baseline will be summarized at each scheduled time point. The percent of patients with QTc interval > 450 msec, > 480 msec, or > 500 msec will be summarized as will the percent of patients with QTcF interval increases from Baseline of 30 to 60 msec or > 60 msec.

All important abnormalities in ECG waveform that are changes from the Baseline readings will be reported (e.g., changes in T-wave morphology or the occurrence of U-waves).

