5.4.2. Clinical Laboratory Assessments

Descriptive summaries of selected (quantitative) clinical laboratory results and change from baseline will be presented by treatment group and visit. Laboratory abnormalities will be determined using pre-defined normal ranges. The number and percentage of patients experiencing TE clinically significant (CS) laboratory abnormalities as reported by the central laboratory, and potentially clinically significant (PCS) abnormalities for select parameters per the table below will be summarized by treatment group. Additionally, shifts in Laboratory values with reference to the normal range from Study Baseline to Week 6 will be summarized by treatment group.

Listings will be provided for patients with any laboratory results outside the reference ranges, as well as for patients with any CS and PCS (select parameters) laboratory results.

Criteria for Potentially Clinically Significant Laboratory Tests

Laboratory Parameter	SI Units	Conversion Factor^a	Traditional Units	PCS Criteria^b Low Values	PCS Criteria^b High Values
Hematology					
Hemoglobin	F	g/L	0.1	g/dL	< 100
	Male				< 120
Hematocrit	F	ratio	100	%	≤ 32% and ≥3% decrease from baseline
	Male				≤ 37% and ≥3% decrease from baseline
White cell count		10 ⁹ /L	1	10 ³ /μL	≤ 2.5
Eosinophils absolute cell count		10 ⁹ /L	1	10 ³ /μL	—
Neutrophils absolute cell count		10 ⁹ /L	1	10 ³ /μL	≤ 1.50
					≥ 15
					≥ 1.50
					≥ 12.0

Lymphocyte absolute cell count	10 ⁹ /L	1	10 ³ /μL	≤ 0.8	≥ 4.0
Platelet count	10 ⁹ /L	1	10 ³ /μL	≤ 75	≥ 700
Chemistry					
Albumin	g/L	0.1	g/dL	< 28	—
Alkaline phosphatase	U/L	1	U/L	—	≥ 2 × UNL
ALT	U/L	1	U/L	—	≥ 3 × UNL
AST	U/L	1	U/L	—	≥ 3 × UNL
Blood urea nitrogen	mmol/L	2.8011	mg/dL	—	> 1.4 × UNL
Calcium	mmol/L	4.008	mg/dL	< 1.97	> 2.77
Cholesterol	mmol/L	38.6698	mg/dL	—	> 7.75
Creatinine	μmol/L	0.0113	mg/dL	—	> 1.4 × UNL
Glucose, fasting	mmol/L	18.015	mg/dL	< 3.0	> 7.6 × UNL
Potassium	mmol/L	1	mEq/L	< 3.3	> 5.5
Sodium	mmol/L	1	mEq/L	< 130	> 150
Total bilirubin	μmol/L	0.0585	mg/dL	—	> 1.5 × UNL
Urinalysis					
Protein	—	—	—	—	≥ 2 +
Glucose	—	—	—	—	≥ 1 +

^a Conversion factor is the multiplication factor to convert from SI units to traditional units.

^b Criteria refer to SI units.

LNL = lower normal limit of laboratory reference range; PCS = potentially clinically significant; SI = *Le Système International d'Unités* (International System of Units); UNL = upper normal limit of laboratory reference range.

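### Two SAP safety summaries are wrong as written: the QTcF rows labelled > 450 and > 480 msec are counted as bands, and the high fasting-glucose limit is printed as 7.6 times the upper normal limit

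*SAP*

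**What the plan says.** **QTcF.** Protocol 10.8.4 sets three categories, with no split by sex and no rule against counting a patient in more than one: "The percent of patients with QTc interval > 450 msec, > 480 msec, or > 500 msec will be summarized". For change from Baseline it uses 30 to 60 msec and > 60 msec.

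SAP 5.4.4 assigns patients to their worst category: "For these summaries, worst-case assignments will be made to ensure patients with such values are not counted more than once". Its example is that a patient above 500 msec "will count once in the > 500 msec category and will not appear in the > 450 or > 480 msec categories". The ECG criteria table just above that paragraph uses other limits: > 450 msec for men and > 470 msec for women on the observed value, plus 30-60, > 60 and > 500. It has no 480 limit, although the paragraph below it refers to a > 480 category. SAP section 9 lists both a QTcF category table (14.3.5.3.2) and a table of significant ECG abnormalities (14.3.5.4). It does not say which set of limits builds which table.

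**Glucose.** SAP 5.4.2 says that "potentially clinically significant (PCS) abnormalities for select parameters per the table below will be summarized by treatment group". In that table, fasting glucose is in mmol/L, with a low limit of < 3.0 and a high limit of > 7.6 × UNL. A footnote says the criteria refer to SI units.

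SAP section 7 says that no deviations from the planned analysis are anticipated, so neither item is presented as a deliberate change.

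**The concern.** A row labelled > 450 msec will be read as the percentage of patients above 450 msec. Under the SAP rule it is the percentage between 450 and 480. A reader who compares arms on that row alone gets too low a figure. The figure also moves the wrong way when patients worsen: someone who goes from the 451-480 range to above 480 leaves the > 450 row.

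QTcF is a natural focus here. The protocol reports hERG block in vitro (section 1.3.2) and mainly positive mean QTcB changes at 3 and 7.5 mg in the multiple-dose study (section 1.4), and two of the withdrawal criteria in section 9.2 rest on QTcF.

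For glucose, the by-arm PCS count is meant to show whether marked elevations differ between arms. A limit that almost no value could reach makes that count uninformative. Protocol 10.8.2 leaves the markedly abnormal limits to the SAP, so no other document corrects the entry.

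**Working it through.** The plan gives no derived figure to reproduce here. The check is a comparison of texts plus simple counting.

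**QTcF, general form.** Let a, b and c be the numbers of patients whose worst QTcF is > 450 to 480, > 480 to 500, and > 500 msec. The SAP's example covers only the > 500 patient. I apply the same worst-case rule to the > 480 patient.

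| Row label | Count the label implies | SAP count | Shortfall |
|---|---|---|---|
| > 450 | a + b + c | a | b + c |
| > 480 | b + c | b | c |
| > 500 | c | c | 0 |

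**QTcF, example.** The arm size of 81 is the planned number per MIN-117 dose (Protocol 10.1). The QTcF counts are invented for illustration: 6 above 450, of whom 2 exceed 480 and 1 of those exceeds 500. So a = 6 − 2 = 4, b = 2 − 1 = 1, c = 1.

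- Rows as labelled: 6, 2, 1, which is 6/81 = 7.4%, 2/81 = 2.5%, 1/81 = 1.2%.
- Rows under the SAP rule: 4, 1, 1, which is 4/81 = 4.9%, 1/81 = 1.2%, 1/81 = 1.2%.
- If one of the four patients at 451-480 worsens to 481-500, the SAP rows become 3, 2, 1. The > 450 row falls from 4.9% to 3/81 = 3.7%. The cumulative > 450 count stays at 6.

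**QTcF, which limits apply.** Take nine invented patients: men at 440, 455, 485 and 505 msec; women at 455, 465, 475, 490 and 510 msec.

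- SAP rows > 450 / > 480 / > 500: 4 / 2 / 2.
- Cumulative rows: 8 / 4 / 2.
- The sex-specific observed-value flag catches 6 of the 8 patients above 450. The two it does not catch are the women at 455 and 465. Both are counted in the unsplit > 450 row.

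The two sets of limits therefore give different counts, and the SAP should say which one builds Table 14.3.5.3.2.

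**Glucose, internal comparison.** The other UNL-based limits in the table are 1.4 (blood urea nitrogen, creatinine), 1.5 (total bilirubin), 2 (alkaline phosphatase) and 3 (ALT, AST). Calcium, potassium and sodium have a low and a high limit, both absolute. Glucose alone pairs an absolute low limit with a UNL multiple on the high side, and 7.6 is more than twice the next largest multiple (7.6 / 3 = 2.5).

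**Glucose, size.** The documents give no fasting-glucose UNL. I assume 5.5 to 6.1 mmol/L and use the table's own conversion factor, 18.015.

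- As printed: 7.6 × 5.5 = 41.8 mmol/L and 7.6 × 6.1 = 46.4 mmol/L. Converted before rounding, these are 753 and 835 mg/dL.
- Read as an absolute SI value: 7.6 mmol/L × 18.015 = 137 mg/dL. That is 7.6 / 6.1 = 1.25 to 7.6 / 5.5 = 1.38 times the assumed UNL.

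**The case against.** The strongest reply on QTcF is that worst-category counting is a legitimate display and the SAP discloses it. A reader might infer that the most prolonged patients disappear from the report. They do not: a patient above 500 msec is in the > 500 row of the same summary, and adding the rows recovers the cumulative counts (4 + 1 + 1 = 6). When the > 450 row falls because someone worsens, the next row rises by the same number. The protocol's change categories of 30 to 60 and > 60 msec are already exclusive, and nothing in Protocol 10.8.4 forbids exclusive counting. All of this stands. What remains is that the labels say one thing and the counts another, while the plain reading of the protocol is cumulative.

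A reader might also infer that women at 451-470 msec go unreported. The documents do not support that. The 470 limit belongs to the PCS flag and matches the protocol's own exclusion criterion 18, "QTcF interval at Screening or Baseline greater than 450 msec for males and 470 msec for females". The worst-case paragraph names a > 450 category without a sex split, which counts these women. The 30-60 and > 60 msec change criteria can also flag them, and all ECGs are listed. It would become a gap only if Table 14.3.5.3.2 were built from the sex-specific limits, which the SAP does not say.

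On glucose, a reader might infer that high values would be hidden. They would still appear in the summaries by visit, the shift table to Week 6, the abnormalities that the central laboratory reports as clinically significant, and the out-of-range listing. Urine glucose of 1+ or more is a separate PCS criterion. That stands, but none of these replaces a by-arm count against a usable fasting-glucose limit.

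Finally, the background should not be read as an established QT signal. The protocol also reports no QTc effect in monkeys up to 100 mg/kg. It says the QTcB changes could be explained by heart rate, judged them not clinically relevant, and reports no QTcB above 480 msec.

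**Conclusion.** The point holds for two items.

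1. **QTcF rows.** The > 450 and > 480 rows understate the percentages their labels name, by exactly the number of patients in the higher rows. In the illustrative arm of 81, the > 450 row shows 4.9% instead of 7.4%. The mechanism follows from the text; the patient counts are invented. The criteria table and the paragraph below it also disagree about a 480 limit. This is a fault of labelling and specification, and no data are lost.

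2. **Glucose limit.** As printed, > 7.6 × UNL does not fit the rest of the table. Under an assumed UNL of 5.5 to 6.1 mmol/L, the flag needs about 42 to 46 mmol/L and would almost certainly be empty in every arm. The multiplier looks like a stray addition to an absolute SI value. That is an inference from the other rows, and only the source of the criteria can confirm it.

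The sex-specific 450/470 limit is not an error. These are descriptive safety tables, so the primary efficacy conclusion is unaffected. The changes should still be made, because programs that followed the SAP exactly would produce misleading rows.

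**What to change.** **SAP 5.4.4.** Choose one of two options:
- count cumulatively, so that > 450, > 480 and > 500 msec each include all higher values, as Protocol 10.8.4 reads; or
- keep worst-case counting and relabel the rows > 450 to 480, > 480 to 500, and > 500 msec.

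State that Table 14.3.5.3.2 uses the protocol's 450/480/500 categories without a sex split, and report the sex-specific 450/470 PCS flag separately. Reconcile the criteria table with the paragraph below it on the 480 limit.

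**SAP 5.4.2.** Check the high fasting-glucose entry against the source of the criteria and correct it. If the source gives an absolute SI value, remove the multiplier. If it gives a UNL multiple, print that multiple.

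**Cost.** A few lines of SAP text, two table edits and small program changes, made before unblinding. No new data and no change to study conduct.
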